2.3 Determination of sample size

No formal sample size calculation is required for a hepatic insufficiency study. Up to 24 study participants will be included with approximately 12 participants per cohort; this is considered sufficient to meet the study objectives.

Based on the FDA (FDA Guidance for Industry, 2003) regarding a two-fold change in AUC, exploratory sample size estimation was performed assuming the following:

- Log-normal distribution on AUC_{ss}
- Inter-study participant CV% of 40%
- Detection of a two-fold change in AUC_{ss} , which is equivalent to a 50% reduction in total body clearance

A sample size of 12 in each group will have >90% power to detect a fold change in means (expected ratio) of 2.000 assuming that the CV is 0.400 using a 2-sample t-test with a 0.050 1-sided significance level.

3 DATA ANALYSIS CONSIDERATIONS

3.1 General presentation of summaries and analyses

Statistical evaluation will be performed by ICON PLC and supervised by UCB. The datasets will follow the UCB analysis data model (ADaM) data specifications. All statistical analyses will be performed using SAS[®] Version 9.4 or later (SAS Institute, Cary, NC, USA).

Pharmacokinetic parameters will be determined by non-compartmental analysis (NCA) with Pharsight Phoenix WinNonlin[®] v6.3 or higher (Certara L.P., Princeton, NJ, NCA) for PK parameter estimation using actual doses administered and the actual sampling times relative to time of dose administration.

Categorical endpoints will be summarized using number of study participants (n), frequency, and percentages. Missing data will not be imputed. Individual plasma and urine concentration and PK parameters will be presented using 3 significant digits.

When reporting relative frequencies or other percentage values, the following rules apply:

- For values where all study participants fulfill certain criteria, the percentage value will be displayed as 100
- For values where the absolute frequency is zero, there will be no percentage displayed
- All other percentage displays will use 1 decimal place

Percentages displayed based on continuous data (e.g. percentage changes from baseline) will be displayed to 1 decimal place. Unless otherwise stated, the denominator for the percentages will be based on the number of participants in the respective analysis set.

Continuous variables will be summarized by visit and time point (where applicable) including number of study participants (n), mean, median, standard deviation (sd), minimum and maximum. Geometric coefficient of variation (geoCV), geometric mean and 95% confidence interval (CI) for the geometric mean will also be presented in the descriptive statistics for the plasma concentration and PK parameters for PSL and two of its metabolites (██████████) and ██████████. In all outputs, the confidence limits will be restricted to the possible values that the variable can take.

When reporting descriptive statistics, the following rules will apply in general except for PK concentration data (plasma and urine PK) of PSL and two of its metabolites ([REDACTED] and [REDACTED])::

- n will be an integer
- Mean (arithmetic and geometric), standard deviation and median will use 1 decimal place more, or 1 significant figure more – depending on the reporting format of the original data – than the original data
- Confidence intervals will use 1 decimal place more, or 1 significant figure more – depending on the reporting format of the original data – than the value around which the confidence interval is constructed
- Coefficient of variation (CV) will be reported as a percentage to 1 decimal place
- Minimum and maximum will be reported using the same number of decimal places or significant figures as the original value
- If no participants have data at a given time point, then only n=0 will be presented. If n<3, then only the n, minimum and maximum will be presented. If n=3, then only n, minimum, median and maximum will be presented. The other descriptive statistics will be left blank.

When reporting individual values and descriptive statistics for PK concentration data (plasma and urine PK of PSL and two of its metabolites [REDACTED] and [REDACTED]), the following rules will apply regarding rounding and precision:

- Individual values for PK concentration data will be reported to the same level of precision as received from the bioanalytical laboratory
- Descriptive statistics for PK concentration data will be reported to the same level of precision as the individual data for the minimum and maximum, and to 1 additional decimal place or 1 additional significant figure– depending on the reporting format of the original data with a maximum of 3 significant digits - for the mean (arithmetic and geometric), median and standard deviation. The 95% CI for the geometric mean will use 1 decimal place more, or 1 significant figure more – depending on the reporting format of the original data – than the value around which the confidence interval is constructed
- Geometric CV will be reported as a percentage to 1 decimal place

When reporting individual values and descriptive statistics for PK parameters (plasma and urine PK of PSL and two of its metabolites ([REDACTED] and [REDACTED] and metabolite to parent ratio) the following rules will apply with regard to rounding and precision:

- Individual values for PK parameters will be reported to 3 significant figures
- Descriptive statistics for PK parameters should be rounded to 4 significant figures for the mean, median and standard deviation and to 3 for the others

Data listings containing all documented data and all derived data will be generated and presented by cohort (healthy participants and participants with moderate hepatic impairment) and treatment period.

3.2 General study level definitions

3.2.1 Relative day

The relative day of an event will be derived with the date of first dose of investigational medicinal product (IMP), PSL, as reference.

Relative days for an event or measurement occurring before the date of first dose are calculated as follows:

$$\text{Relative Day} = \text{Event Date} - \text{Date of First Dose}$$

The relative day for an event or measurement occurring on the date of first dose (Single Dose treatment period) is 1. The relative day for an event or measurement occurring on or after the date of first PSL dose to the date of the last dose will be calculated as follows:

$$\text{Relative Day} = (\text{Event Date} - \text{Date of First Dose}) + 1$$

For events or measurements occurring after the date of last dose, relative day will be prefixed with '+' in the data listings and will be calculated as follows:

$$\text{Relative Day} = + (\text{Event Date} - \text{Date of Last Dose})$$

There is no relative Day 0. Relative day will not be calculated for partial dates in cases where relative day is shown in a participant data listing. In such cases, relative day should be presented as '--' in the relevant participant data listing.

3.2.2 Study periods

For each participant completing the study, the expected maximum duration of participation will be approximately 46 days with a maximum of 6 days exposure to investigational product, and will consist of the following periods:

- Screening/Baseline Period (Day -28 to Day -1)

The Screening Period consists of a single Screening Visit, which will be conducted at the unit within 28 days prior to check-in for treatment period, and a Baseline Visit, which will be conducted at the clinical research unit (CRU) 1 day prior to treatment period (on Day -1). Study participants will check-in at the CRU on Day -1.

- PSL Single Dose Administration Period (Day 1 to Day 7)

In the Single Dose Period, study participants will receive a single oral dose of 100mg PSL on Day 1, at approximately 8:00am, 30 minutes after a light meal has finished. No study drug will be administered on Days 2 to 7; assessments will be conducted during this time as specified in the Schedule of Activities (Table 2-). Days 2 to 7 are designated as a 6-day washout.

- PSL Multiple Dose Administration Period (Day 8 to Day 17)

In the Multiple Dose Period, study participants will receive multiple oral PSL doses on Days 8 to 12, followed by a 5-day washout (Days 13 to 17). Padsevonil will be administered BID, with one 100mg dose in the morning [approximately 8:00am] and one 100mg dose in the evening [approximately 8:00pm] on Days 8 to 11. One dose of 100mg of PSL will be administered on the morning of Day 12. The Follow-Up Period consists of an End of Study (EOS)/Early Termination Visit (ETV) performed after discharge on Day 18 or upon discontinuation of the study.

The end of the study is defined as the date of the last visit of the last participant in the study.

3.3 Definition of Baseline values

Baseline will be the last non-missing value prior to first PSL dosing in the Single Dose Period on Day 1. Scheduled or unscheduled measurements can be used as the Baseline value.

If a measurement is repeated at Baseline and is obtained prior to dosing, then the last available measurement will be used as the Baseline value.

Variable	Baseline definition
Hematology, serum, chemistry, urinalysis	The baseline value is defined as the value on Day -1. If the baseline value is missing, the value obtained at Screening will be used.
Vital signs	The baseline value is defined as the value on predose on Day 1. If this value is missing, the last value prior dosing will be used.
ECG	12-lead ECG will be measured in triplicate. Baseline is the mean of the last three measurements on Day -1. If less than three replicates are available, the mean of the available replicates (prior to dosing) will be considered as baseline.
C-SSRS	The baseline value is defined as the value from Day -1. If the baseline value is missing, the value obtained at Screening will be used.

The change from Baseline to any subsequent post-Baseline visit will be calculated as the simple difference between that post-Baseline visit's value and the Baseline visit value, as below:

$$\text{Change from Baseline} = \text{Post Baseline Visit Value} - \text{Baseline Visit Value}$$

3.4 Protocol deviations

Important protocol deviations (IPD) are deviations from the protocol which potentially could have a meaningful impact on study conduct or on the primary PK outcome for an individual study participant. Study participants will be excluded from FAS only when there is documented evidence that they received no treatment. Study participants may be excluded from the PKS if they had an important protocol deviation affecting the PK parameters.

The criteria for identifying protocol deviations and the classification of protocol deviations will be captured in the Important Protocol Deviations document. To the extent feasible, rules for identifying protocol deviations will be defined without review of the data and without consideration of the frequency of occurrence of such deviations. Whenever possible, criteria for identifying important protocol deviations will be implemented algorithmically to ensure consistency in the classification of important protocol deviations across all study participants.

Important protocol deviations will be reviewed as part of an ongoing data cleaning process prior to database lock to confirm exclusion from analysis sets. After all data have been verified/coded/entered into a database, a data evaluation meeting (DEM) will be held.

At least one DEM will be performed at the following time:

- Prior to the final analysis after all data have been verified/coded/entered into the database

Additional DEMs may be conducted as deemed necessary.

The purpose of these DEM reviews will be to review all protocol deviations, determine whether the deviations are considered important or not important, define the analysis sets, and check the quality of the data. The reviews will also help decide how to manage problems in the participants' data (e.g., missing values, withdrawals and protocol deviations).

Accepted deviations from scheduled time points will be described in the appropriate documents and included in the Study Master File. After the pre-analysis review, resolution of all issues, and documentation of all decisions (including inclusion into each of the analysis sets) at the final DEM, the database will be locked.

3.5 Analysis sets

3.5.1 All Study Participants

All Study Participants consists of all study participants who have signed the Informed Consent Form (ICF).

3.5.2 Safety Analysis Set

The Safety Set (SS) consists of all study participants who received at least one dose of the investigational medicinal product (IMP). Study participants will be classified according to the treatment which was actually received. All safety analyses will be performed using the Safety Set.

3.5.3 Full Analysis Set

The Full Analysis Set (FAS) consists of all study participants who have received at least one dose of the IMP and have at least one valid post-baseline primary assessment observation. Study participants will be classified according to the treatment which was actually received.

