### **9.1 Definition of analysis sets**

The following are the defined analysis sets:

- Enrolled Set: All study participants who have signed the informed consent.
- Full analysis Set (FAS): All enrolled study participants who received at least one dose of study medication. Analysis of this set will be according to the treatment the participants actually received.
- Pharmacokinetic Per Protocol Set (PK-PPS): the PK-PPS is a subset of the FAS, consisting of those study participants who had no important protocol deviations affecting the PK parameters and for whom a sufficient number of samples are available to determine at least one PK parameter.

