#### **9.5 Handling of protocol deviations**

Important protocol deviations are deviations from the protocol that potentially could have a meaningful impact on study conduct or on the primary PK outcomes for an individual study participant. Furthermore, study participants will be excluded from the FAS only when there is documented evidence that they received no treatment. The criteria for identifying important protocol deviations and the classification of important protocol deviations will be defined within the relevant protocol deviation specification document, which is part of the study Data Cleaning Plan. To the extent feasible, rules for identifying protocol deviations will be defined without review of the data and without consideration of the frequency of occurrence of such deviations. Whenever possible, criteria for identifying important protocol deviations will be implemented algorithmically to ensure consistency in the classification of important protocol deviations across all study participants.

Important protocol deviations will be reviewed as part of an ongoing data cleaning process prior to database lock to confirm exclusion from analysis sets.

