5 STUDY POPULATION CHARACTERISTICS

5.1 Participant disposition

The number of participants who signed the informed consent, participants who completed or prematurely discontinued the study, as well as the reason for discontinuation will be summarized for all participants, based on the SS. A participant who completed the study is defined as a study participant who completed all visits up to and including the EOS/ETV visit (in the Follow-up Period). If there is more than one termination due to AE, then an additional table summarizing the discontinuations due to AE will be produced. In case that only one subject discontinues due to AE, then this will be presented in a listing.

The number and percentage of study participants included in each of the analysis sets will be summarized based on All Study Participants. Percentages will be calculated based on All Study Participants for the purpose of this summary.

Screening failure reasons will be listed for the All Study Participants.

In addition, the following listings will be presented:

- Participant disposition (All Study Participants)
- Participant analysis sets (All Study Participants)

The listing of participant disposition will include the date of informed consent, date and time of first and last dose of study medication, date of premature termination and primary reason (if applicable).

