5.2 Protocol deviations

Important protocol deviations will be identified and classified by the deviation types in the IPD document (see also section 3.4). A listing of all IPDs identified at the DEM will be presented by cohort for all participants based on the FAS and will include the deviation type and description.

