6.2 Other Baseline characteristics

The criteria to determine the Child-Pugh score will be summarized for all participants by cohort and overall based on the FAS. This includes total serum bilirubin (mg/dL), serum albumin

(g/dL), prothrombin time (sec prolonged/international normalized ratio (INR)), ascites, hepatic encephalopathy, total points and hepatic insufficiency classification.

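### SAP 3.5.3 adds a valid primary observation to the FAS definition, against SAP 3.4 and protocol 9.1 and 9.5, so a dosed participant can drop out of three FAS-based outputs

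*SAP*

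**What the plan says.** The documents give two different rules for who belongs to the FAS.

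- Protocol 9.1 defines the set as "All enrolled study participants who received at least one dose of study medication". Protocol 9.5 adds that "study participants will be excluded from the FAS only when there is documented evidence that they received no treatment".
- SAP 3.4 repeats that rule: "Study participants will be excluded from FAS only when there is documented evidence that they received no treatment".
- SAP 3.5.3 restricts the set to participants who "have received at least one dose of the IMP and have at least one valid post-baseline primary assessment observation". The SAP does not define what makes an observation valid. The primary variables (SAP 9.1) are all plasma PK parameters.

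SAP 3.9 records two renamed sets and a new Safety Set, but no change to the FAS. The Safety Set (SAP 3.5.2) needs one dose only.

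Three outputs use the FAS. The listing of important deviations "will be presented by cohort for all participants based on the FAS" (SAP 5.2). The demographic characteristics are summarised on the FAS (SAP 6.1). The Child-Pugh criteria "will be summarized for all participants by cohort and overall based on the FAS" (SAP 6.2). The AE-duration table in SAP 4.2.4 also refers to the FAS: when the onset day and time are missing, it supplies a substitute start for FAS participants and for screen failures, and for nobody else.

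On disposition, SAP 5.1 says that the number who signed consent, completion, early discontinuation, "as well as the reason for discontinuation will be summarized for all participants, based on the SS".

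**The concern.** SAP 3.4 and SAP 3.5.3 cannot both be followed for a participant who took study drug but has no valid primary PK observation. Under 3.4 that person must be in the FAS, and under 3.5.3 cannot be. The general clause in SAP section 1, that the protocol applies unless the SAP says otherwise, does not settle this, because the SAP itself says two things.

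The choice matters for reporting. The cohorts are not randomised (protocol 6.3), so readers use the baseline summaries to judge comparability and the deviation listing to understand exclusions. If a deviation is what left a participant without valid PK, 3.5.3 would remove that person from the listing meant to document it. Because validity is undefined and the data evaluation meeting settles the analysis sets (SAP 3.4) in an open-label study, 3.5.3 also brings a judgement into a set that the protocol fixes by dosing.

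The disposition table has a separate and smaller fault: a count of people who signed consent is taken within a set that contains only dosed people.

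**Working it through.** **Step 1. The definitions side by side.**

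| Place | Condition for the FAS |
|---|---|
| Protocol 9.1 | at least one dose |
| Protocol 9.5 | out only if documented as untreated |
| SAP 3.4 | out only if documented as untreated |
| SAP 3.5.3 | at least one dose and at least one valid post-baseline primary observation |

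Three of the four agree. The fourth is narrower and is not declared in SAP 3.9.

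**Step 2. Trace one participant through the outputs.** Take someone who is dosed on Day 1 and has no valid primary PK observation, and apply SAP 3.5.3 as written.

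| Output | Set used | Participant present? |
|---|---|---|
| Important-deviation listing (SAP 5.2) | FAS | no |
| Demographic summary (6.1) | FAS | no |
| Child-Pugh summary (6.2) | FAS | no |
| AE duration when onset is missing (4.2.4) | FAS or screen failure | no rule applies |
| Demographic listing (6.1) | All Study Participants | yes |
| Disposition and analysis-set listings (5.1) | All Study Participants | yes |
| Analysis-set count table (5.1) | All Study Participants | yes, counted in the Safety Set but not in the FAS |
| Medical history, medications, safety outputs (6.3, 6.4, 10) | Safety Set | yes |
| PK analyses (3.5.4, 9) | PK Set | no, under either FAS definition |

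The last row holds under either definition because the PK Set already requires at least one PK parameter to be determinable.

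**Step 3. Size.** With 12 per cohort, one such participant is 1/12 = 8.3% of a cohort, or 1/24 = 4.2% of the study.

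**Step 4. Power.** Inputs from protocol 9.8: 12 per group, ratio 2, CV 0.40, one-sided alpha 0.05.

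- Log-scale SD = sqrt(ln(1 + 0.40²)) = 0.3853; difference = ln 2 = 0.6931.
- Noncentrality = 0.6931 / (0.3853 × sqrt(1/12 + 1/12)) = 4.41, with 22 df.
- Exact power is 99.6% (99.7% by the normal approximation), which agrees with the plan's statement of more than 90%.
- With 12 against 11, exact power is 99.4%.

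The loss of one participant from the PK comparison would barely move power, and that loss would occur under either FAS definition.

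**Step 5. The consent count.** Everyone in the Safety Set was dosed, and everyone dosed must first have signed consent. Within that set, the number who signed consent equals the number dosed, whatever the number screened. The same section (SAP 5.1) also gives an analysis-set summary whose denominator is All Study Participants, meaning everyone who signed consent (SAP 3.5.1), and a listing of screen-failure reasons on that set. The consented total is therefore available elsewhere in 5.1.

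**The case against.** The strongest reply is that the affected case is narrow and leaves traces. Participants are confined to the clinic until Day 18, site staff give the drug, and 11 post-dose PK samples fall in the first 12 hours, starting at 15 minutes. A dosed participant with no valid primary observation at all is unlikely. Under SAP 3.4 and 3.5.4, an important deviation affecting PK removes someone from the PK Set, not from the FAS, so most PK exclusions would still appear in the deviation listing. The Safety Set keeps the protocol's dose-only condition for the safety analyses, and SAP 3.9 declares it. All of this stands, and it limits the consequence. It does not remove the contradiction between two SAP sections.

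A reader might infer more than the documents support:

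- *That the participant disappears from the report, or that selective loss in one cohort is hidden.* The listings and Safety Set outputs in Step 2 still show the person. SAP 3.6 presents tables by cohort, so the analysis-set table would show the gap between the Safety Set and the FAS in that cohort. What is lost is a place in three outputs.
- *That a deviation is why the PK is missing.* It may be. An early withdrawal for an adverse event or a withdrawn consent could have the same result.
- *That the consent wording hides the screen failures.* It misstates one count in one table. Other parts of SAP 5.1 report the consented total and list the reasons for screen failure. The documents give no screen-failure rate from which to size an understatement.

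**Conclusion.** The contradiction is real and should be corrected before database lock. As written, SAP 3.5.3 departs from the protocol and from SAP 3.4 without being declared. It would drop a dosed participant without valid primary PK from the important-deviation listing, the demographic summary and the Child-Pugh summary, and leave that participant outside the AE-duration rule for a missing onset.

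The consequence is incomplete reporting in those places. The documents give no probability for the case, and the conclusion does not need one. The primary comparison and its power are practically unaffected. The fault in SAP 5.1 is confined to one count in the disposition table.

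This rests on the SAP text as published. The two protocol clarification memos that SAP section 1 cites were not available; they could not make SAP 3.4 and 3.5.3 agree as they now read.

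**What to change.** 1. In SAP 3.5.3, return to the dose-only FAS. Its membership then equals that of the Safety Set, and the three outputs and the AE-duration rule need no further change. Alternatively, keep the narrower FAS, state what a valid observation is, base the important-deviation listing, demographic summary, Child-Pugh summary and AE-duration rule on the Safety Set, and amend SAP 3.4 to match.
2. Declare in SAP 3.9 any difference from protocol 9.1 and 9.5 that remains.
3. In SAP 5.1, take the signed-consent count in the disposition table from All Study Participants, and keep the Safety Set for completion and discontinuation.

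The cost is SAP wording and the matching population labels in the table and listing specifications. No sample size, data collection or primary analysis changes.
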